5.3 General Concomitant Medication and Supportive Care Guidelines

Because MK-2206 is metabolized by CYP3A4, the case report form must capture the concurrent use of all other drugs, over-the-counter medications, or alternative therapies. The Principal Investigator should be alerted if the patient is taking any agent known to affect or with the potential to affect selected CYP450 isoenzymes. A list of agents known to interact with the CYP3A4 isoform is listed in [Appendix C](#).

Drugs known that may prolong the QTc interval should be avoided.

Everolimus is a substrate of CYP3A4 and a substrate and inhibitor of P-glycoprotein. Everolimus metabolism may be affected by drugs that are substrates or strong inhibitors or inducers of CYP3A4 or P-glycoprotein. A list of agents known to interact with the CYP3A4 and P-glycoprotein are listed in [Appendix C](#).

5.4 Definition of Dose-Limiting Toxicity

A dose limiting toxicity is any grade 3 or 4 hematological or nonhematological toxicity, as well as the following:

1. Grade 3 hyperglycemia that can be brought down to grade 1 within a week (both

- agents).
2. Persistent refractory grade 2 rash (MK2206) despite dose withholding followed by reinitiation at same dose.
 3. Persistent refractory grade 2 nonhematological toxicity (everolimus) that persists despite dose withholding followed by reinitiation at same dose
 4. Persistent refractory grade 2 thrombocytopenia (everolimus) that persists despite dose withholding followed by reinitiation at same dose
 5. Grade 2 pneumonitis (everolimus)

The following will not be considered a dose limiting toxicity

6. Asymptomatic hyperuricemia any grade
7. Asymptomatic lymphopenia, any grade

Management and dose modifications associated with dose limiting toxicities are outlined in [Section 6](#).

5.5 Duration of Therapy

In the absence of treatment delays due to adverse events, treatment may continue until one of the following criteria applies:

- Disease progression,
- Intercurrent illness that prevents further administration of treatment,
- Unacceptable adverse events(s),
- Patient decides to withdraw from the study, or
- General or specific changes in the patient's condition render the patient unacceptable for further treatment in the judgment of the investigator.
- Pregnancy

5.6 Duration of Follow Up

Patients will be followed for every 3 months (by telephone, e-mail, clinic visit, or medical record review) after removal from study until death, whichever occurs first. Follow up of a treatment arm will cease once median OS has been reached for that arm. Patients removed from study for unacceptable adverse events will be followed until resolution or stabilization of the adverse event.

If a patient becomes pregnant while on trial and withdraws, the outcome of the pregnancy will be recorded, including the newborn if the pregnancy is carried to full term.

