5.7 Criteria for Removal from Study

Patients will be removed from study when any of the criteria listed in [Section 5.5](#) applies. The reason for study removal and the date the patient was removed must be documented in the Case Report Form.

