13.2 Sample Size/ Power Calculation

Assuming that the median progression-free survival (PFS) is 4.9 months and 8.2 months for the everolimus and MK2206 arm, respectively and patients will be randomized with 2:1 ratio into the MK2206 arm and the everolimus arm, then with a total of 75 events (i.e., disease progression or death), we will have an 80% power to detect such a 67% increase in median PFS using one-sided log-rank test and at a 0.10 significance level. The total number of patients to be enrolled will be 105, with 35 on the everolimus arm and 70 on the MK2206 arm. The above calculation also assumes an accrual rate of 4 patients per month, thus it will take 26.3 months to accrue all 105 patients. The maximum study duration will be around 29 months, which include patients' accrual period and a follow-up period. East5 software was used for the sample size/power calculation.

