13.4 Statistical Analysis Plan

The primary endpoint, progression-free survival (PFS), is defined as the time interval between date of treatment and date of disease progression, date of death or last follow-up date, whichever occurred first. The probability of PFS be estimated using the Kaplan-Meier method and will be compared between the two treatment arms using stratified log-rank test. Patients' safety data will be summarized by treatment arm, category, severity and relevance.

For secondary analyses, the Kaplan-Meier method will be used to estimate overall survival (OS) and time to failure (TTF), and stratified log-rank test will be used to compare between the two treatment arms. The OS is defined as the time interval between the date of treatment and the date of death or last follow-up, whichever occurred first. The TTF is defined as the time interval between the date of treatment and the date of disease progression, date of death, date of treatment discontinuation due to severe toxicity or last follow-up date, whichever occurred first. Overall response (OR) is defined as CR+PR and logistic regression model will be fit to assess the effect of treatment on the rate of OR.

Since the correlative studies being performed are by nature exploratory, and have not been

performed before in patients with RCC receiving mTOR inhibitors or AKT inhibitors, powering of these endpoints is not possible. Clinical benefit is defined as CR+PR+SD and again, we will fit logistic regression models to assess the effects of treatment, AKT activation, circulating cytokines and angiogenic factors, and karyotype on clinical benefit. The interaction effect between treatment and these exploratory factors will also be evaluated.

For virtual karyotyping, technique specific statistical analyses are outlined in [Appendix G](#).

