MIP-1 β
Eotaxin
CTACK
GRO-A
MCP-3
MIF
MIG
TRAIL

Other interleukins

IL-1ra
IL-2
sIL-2RA
IL-3
IL-4
IL-5
IL-7
IL-9
IL-10
IL-13
IL-16
IL-17
IL-18

Growth factors

GM-CSF
G-CSF
M-CSF
SCF
NGF-B

Statistical Analysis:

We have investigated potential blood-based biomarkers in a randomized phase II trial of sorafenib vs. sorafenib and interferon. Using multiplexed bead assays (MBAs) and ELISAs to broadly assess a profile of cytokines and angiogenic factor (CAFs), we have identified plasma markers that predicted improved progression-free survival (PFS) in patients in each arm. A CAF signature, derived by combining individual markers, was more predictive than individual markers alone. *In vitro* studies and patient data suggest that CAFs may be regulated by tumor hypoxia, Akt/mTOR signaling, and other pathways. Based on this and additional studies in other cancer types, we *hypothesize that broad profiling of CAFs in plasma of RCC patients can be used to identify groups of patients that receive different degrees of benefit from different therapeutic regimen*. We also hypothesize that CAF profiling can identify markers of therapeutic resistance and tumor pathway activation. Our primary goal in this project is to develop predictive biomarkers of benefit (prolongation in PFS and overall survival, OS) using plasma specimens from this randomized phase II trial.

For the multiplexed bead arrays, the data is assessed in the following manner. For each plate, the standard curves are assessed to ensure that the expected assay range was achieved. For each individual sample, the mean concentration is calculated for duplicate samples, and the coefficient of variance % (CV%) is calculated for all analytes. If the median CV% was greater than 25%, analysis of the sample is repeated. In the rare case that the repeat CV% was greater than 25%, one of the two analyses is selected based on lower CV% and consistency with prior values.

The multiplexed beads are assessed in a similar manner. For each plate, the standard curves are assessed to ensure that the expected assay range was achieved. For each individual sample, the mean concentration is calculated for duplicate samples, and the CV% is calculated. If the CV% for an individual sample is greater than 50%, the value is rejected.

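### Section 5.6 ends each arm's survival follow-up at that arm's own median OS, with no accrual condition or common date, although section 13.4 compares OS between the arms: a minor defect that is cheap to fix

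*Combined protocol and SAP*

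**What the plan says.** Section 5.6 provides for contact every 3 months "after removal from study until death, whichever occurs first", and then adds: "Follow up of a treatment arm will cease once median OS has been reached for that arm". The first phrase calls for the earlier of two events but names only one. The second does not say how or when the median is judged to be reached, whether enrolment must be complete, or whether the two arms share a date.

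Section 5.7: "Patients will be removed from study when any of the criteria listed in" section 5.5 is met. Disease progression is one of those criteria, so the 3-monthly contacts are the main planned source of deaths after progression.

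Section 13.4: "The OS is defined as the time interval between the date of treatment and the date of death or last follow-up, whichever occurred first". For OS it specifies Kaplan-Meier estimation and that a "stratified log-rank test will be used to compare between the two treatment arms". Sections 13.1 to 13.5 give no OS cut-off date, OS event count, OS median or OS significance level.

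Section 13.2, within the PFS power calculation: "thus it will take 26.3 months to accrue all 105 patients. The maximum study duration will be around 29 months".

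**The concern.** When last follow-up is a censoring time in a between-arm comparison, both arms should normally be followed to one date fixed without regard to either arm's results. Here each arm's end date is a function of its own deaths. The arm with shorter survival tends to stop first, and after that the other arm's deaths add nothing to the comparison.

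If the median is read off an early, immature curve, an arm could stop while patients are still being randomized to it, and most of its deaths would never be recorded. At stake are the secondary OS comparison, the reported OS medians, and the exploratory karyotype and cytokine analyses in Appendices G and I that use OS. A contact that was not made at the time may not be recoverable later.

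**Working it through.** **1. Inputs from the plan.** 105 patients, 70 to MK-2206 and 35 to everolimus, 4 per month (section 13.2). Accrual takes 105/4 = 26.25 months; the plan states 26.3. There is no OS figure to reproduce, so the check starts with the PFS figures.

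**2. What the 29 months is.** With exponential PFS and uniform accrual over A = 26.25 months, the chance of a PFS event by T = 29 is 1 − [exp(−λ(T−A)) − exp(−λT)]/(λA), with λ = ln 2/median.
- Everolimus, median 4.9: 1 − (0.678 − 0.017)/3.713 = 0.822; × 35 = 28.8 events.
- MK-2206, median 8.2: 1 − (0.793 − 0.086)/2.219 = 0.682; × 70 = 47.7 events.

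The total is 76.5, against 75 planned. The 29 months is therefore the time needed for the PFS events and not an OS cut-off. The PFS power itself is Φ(ln(8.2/4.9) × √(75 × 2/9) − 1.282) = Φ(0.82) = 0.794, against the stated 81% (no interim analysis) and 80% (with it). No OS quantity enters this.

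**3. Effect on OS under each reading.** Assumptions, none from the documents: exponential OS, looks every 3 months, unstratified log-rank test at one-sided 0.10. Medians are 15/15 months for error and 15 (everolimus) against 22 for power. There were 8,000 simulated trials per scenario (standard error about 0.004 for error, 0.006 for power). Each cell gives the section 5.6 rule, then a common post-accrual cut-off.

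| Reading | Deaths, 15/15 | Error, 15/15 | Power, 15 vs 22 |
|---|---|---|---|
| Half of the arm's planned patients dead | 56.4 / 59.9 | 0.111 / 0.098 | 0.537 / 0.548 |
| Kaplan-Meier median, only after accrual | 46.5 / 47.2 | 0.102 / 0.102 | 0.457 / 0.472 |
| Running Kaplan-Meier from month 12, whole arm cut | 22.7 / 47.2 | 0.121 / 0.102 | 0.364 / 0.472 |
| Running Kaplan-Meier from month 6, whole arm cut | 19.5 / 47.2 | 0.141 / 0.102 | 0.353 / 0.472 |

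Deaths not collected, row by row: 1 − 56.4/59.9 = 6%; 1 − 46.5/47.2 = 1.5%; 1 − 22.7/47.2 = 52%; 1 − 19.5/47.2 = 59%. In the two running rows the reported medians are 11 to 13 months against a true 15. In the first two rows they are right.

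**4. Running trigger, only post-removal contacts stop.** This assumes PFS median 4.9 and OS median 15 in both arms, patients on treatment observed until removal, 0% to 25% of PFS events being deaths, and 4,000 trials. Deaths are 16.3 to 32.3, against 51.3 to 51.7 at a common cut-off at month 29 or later, so between 1 − 32.3/51.7 = 38% and 1 − 16.3/51.3 = 68% are lost. Error is 0.076 to 0.091 in five of six settings and 0.139 in the sixth. An arm's final curve fails to reach 50% in 22% to 79% of trials.

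**5. Distance between the arms' cut-offs.** Half of planned patients dead, 15/15: median 3 months, 90th percentile 6 to 9 depending on simulation details. After accrual only: median 0, 90th percentile 3.

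**6. Other assumptions.** With everolimus OS 14 months and hazard ratio 0.6, checked monthly once 5 patients are enrolled, the running whole-arm rule gives power 0.36 against 0.62. Half of planned patients dead, assessed continuously, gives 0.69 against 0.72, with the arms ending a median of 8.2 months apart. A stratified test with three assumed strata gives errors of 0.133 (running from month 6), 0.120 (from month 12), 0.115 (half dead) and 0.105 (after accrual), so stratifying does not change the pattern.

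**The case against.** The best defence is that the large losses need a strained reading. Few teams would stop following an arm to which they are still randomizing, and section 13.2 describes an accrual period and a follow-up period, which fits a rule applied after accrual. On that reading, or on half of planned patients dead, the cost is small. If the 29 months is also taken as an outer limit for both arms, half-dead with 15/15 gives a median gap of 0 months, 50.4 deaths against 51.1, and error 0.116 against 0.111. This stands as a limit on size. It does not remove the point, because no section says that the rule waits for accrual and the 29 months belongs to the PFS calculation.

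A reader might infer three stronger things, and the documents support none of them.
- **That the OS log-rank test is invalid.** Unequal censoring alone does not invalidate it. The direction of the error is also unstable: above 0.10 when the whole arm is cut, mostly below it when only post-removal contacts stop.
- **That half the deaths will certainly be lost.** This holds only for a running trigger during accrual.
- **That PFS is damaged.** The rule sits among the contacts after removal from study, and section 5.2 schedules assessments on treatment separately. For the same reason the whole-arm-cut rows, which carry the largest power loss, fit section 5.6 poorly.

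**Conclusion.** The defect in the text is real: each arm's survival follow-up ends on that arm's own deaths, with neither an accrual condition nor a shared date, and section 13.4 then compares the arms. Its size cannot be fixed from the documents. A running trigger during accrual would lose 38% to 68% of the OS deaths, and a whole-arm cut would take power for 15 against 22 months from about 0.46 to 0.36. On the milder readings, error is about 0.10 to 0.12 and the loss is 1 to 2 points of power (about 3 with everolimus OS 14 months and hazard ratio 0.6), with modestly unequal cut-offs. All of this rests on assumed OS medians, look times and significance level. Because OS is secondary and unpowered and primary PFS is untouched, this is a minor, cheap improvement.

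**What to change.** Replace the sentence in section 5.6 with: *Survival follow-up continues in both arms until one common data cut-off, after accrual is complete and once the Kaplan-Meier median OS has been reached in both arms.* In the same edit, repair the preceding sentence so that it names both events it refers to. Name this cut-off in section 13.4 as the date of the OS analysis. State in section 13.2 that the 29 months refers to the PFS analysis and that OS follow-up may run longer.

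Under the assumptions above, the common cut-off falls near month 27 (90th percentile month 30 to 33). The cost, over both arms, is about 5 to 13 extra telephone or record contacts if the rule was already meant to act after accrual. It is about 160 to 200 if the rule would have acted during accrual, which is where most deaths would otherwise be lost. The trigger still depends on the observed deaths, but it now gives both arms the same date.

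If the sponsor means half of the planned patients dead, the text should say so and apply it as one common date, because the Kaplan-Meier trigger would fall earlier (47.2 deaths against 59.9). That version costs about 25 to 30 contacts and puts the cut-off near month 33 to 36 (90th percentile 36 to 42). No sample size or primary analysis changes.

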5.7 Criteria for Removal from Study

Patients will be removed from study when any of the criteria listed in [Section 5.5](#) applies. The reason for study removal and the date the patient was removed must be documented in the Case Report Form.

6. DOSING DELAYS/DOSE MODIFICATIONS

Dose delays and dose modification for MK2206 and for everolimus are outlined in the following sections. Dose withholding, dose reduction or treatment discontinuation will be performed for clinically important grade 3 and 4 toxicities. Dose withholding and/or dose reduction will be performed for selected grade 2 toxicities summarized in [Section 5.4](#) and outlined in detail below.

6.1 MK-2206

| Dose Level | MK2206 Dose |
|-------------------|------------------|
| -2 | 90 mg PO weekly |
| -1 | 135 mg PO weekly |
| 0 (starting dose) | 200 mg PO weekly |

Clinically significant Grade 3 side effects attributable to MK2206 will require dose withholding until grade 1 levels of toxicity are reached. At that point drug can be restarted at the next lower dose level. If after four weeks the toxicity remains completely controlled, dose re-escalation can be attempted at the treating physician's discretion.

If toxicity does not resolve to a grade 1 or lower levels within four weeks of drug discontinuation, the patient will be taken off study.

Clinically significant Grade 4 side effects attributable to MK2206 which are considered medically relevant will result in patient being taken off study.

Management of Hyperglycemia

Grade 3 hyperglycemic events (>250 mg/dL) should lead to consultation with an endocrinologist or other specialist. If glucose levels do not return to grade 1 or lower within one week of appropriate therapy, patients should be considered to have a DLT.

Appropriate therapy will usually involve oral antihyperglycemic agents, since the inhibition of glucose transport into the cell by AKT/mTOR inhibitors may render insulin ineffective. The goal of therapy is to keep fasting glucose <150 mg/dL, random blood glucose levels <180 mg/dL, and Hemoglobin A1c <8%. Glucose monitoring should be performed weekly, during the first cycle of therapy, and on day 1 of subsequent cycles, prior to drug administration.

Hemoglobin A1c monitoring, for patients requiring treatment of hyperglycemia, should be

performed with each cycle of MK-2206 therapy.

Management of Rash

Patients who develop grade 3 rash will have treatment withheld as outlined above. For patients with persistent grade 2 rash that does not respond to conservative measures, and which in the opinion of the treating physician is significantly compromising quality of life, dose can be held, and once rash reaches grade 1 intensity or lower, MK2206 can be restarted at the same dose level. If a second dose withholding is required for redevelopment of persistent refractory grade 2 rash, dose can be withheld and then restarted at one dose level lower once rash reaches a grade 1 or lower level. MK2206 re-escalation can be attempted after 4 weeks if in the judgment of the treating physician the patient's side effect profile warrants re-escalation.

6.2 Everolimus

Table 3 Everolimus dose level modification guidelines

| Dose level | Dose and schedule |
|-------------------|---------------------|
| 0 (starting dose) | 10 mg daily |
| -1 | 5 mg daily |
| -2 | 5mg every other day |

Table 4 Criteria for dose-modification in case of suspected toxicity and reinitiation of everolimus treatment

| Toxicity | Actions |
|---|--|
| 
Non-hematological toxicity
 
Grade 2 (pneumonitis – refer to Table 5)
 
Grade 3 (hyperlipidemia*) (pneumonitis – refer to Table 5)
 
Grade 4
 | 
If the toxicity is tolerable to the patient, maintain the same dose. If the toxicity is intolerable to patient, interrupt everolimus until recovery to grade ≤ 1.
 
Then reintroduce everolimus at same dose. If event returns to grade 2, then interrupt everolimus until recovery to grade ≤ 1. Then reintroduce everolimus at the lower dose level.
 
Interrupt study drug until recovery to grade ≤ 1. Then reintroduce everolimus at the lower dose level. For pneumonitis consider the use of a short course of corticosteroids.
 
Discontinue everolimus.
 |
| 
Hematological toxicity
 
Grade 2 Thrombocytopenia (platelets $<75, \geq 50 \times 10^9/L$)
 | 
Interrupt study drug until recovery to grade ≤ 1 ($>75 \times 10^9/L$). Then reintroduce study drug at initial dose. If thrombocytopenia again returns to grade 2, interrupt study drug until recovery to grade ≤ 1. Then reintroduce study drug at the lower dose level.
 |

| | |
|---|--|
| Grade 3 Thrombocytopenia (platelets $<50, \geq 25 \times 10^9/L$) | Interrupt study drug until recovery to grade ≤ 1 (platelets $\geq 75 \times 10^9/L$). Then resume study drug at one dose level lower. If grade 3 thrombocytopenia recurs, discontinue study drug. |
| Grade 4 Thrombocytopenia (platelets $< 25 \times 10^9/L$) | Discontinue study drug. |
| Grade 3 Neutropenia (neutrophils $<1, \geq 0.5 \times 10^9/L$) | Interrupt study drug until recovery to grade ≤ 1 (neutrophils $\geq 1.5 \times 10^9/L$). Then resume study drug at the initial dose. If ANC again returns to Grade 3, hold study drug until the ANC $\geq 1.5 \times 10^9/L$. Then resume study drug dosing at the lower dose level. Discontinue patient from study therapy for a third episode of grade 3 neutropenia. |
| Grade 4 Neutropenia (neutrophils $< 0.5 \times 10^9/L$) | Interrupt study drug until recovery to grade ≤ 1 (neutrophils $\geq 1.5 \times 10^9/L$). Then resume study drug at the lower dose level. If grade 3 or grade 4 neutropenia occurs despite this dose reduction, discontinue study drug. |
| Grade 3 febrile neutropenia (not life-threatening) | Interrupt study drug until resolution of fever and neutropenia to grade ≤ 1 . Hold further study drug until the ANC $\geq 1,500/mm^3$ and fever has resolved. Then resume study drug at the lower dose level. If febrile neutropenia recurs, discontinue study drug. |
| Grade 4 febrile neutropenia (life-threatening) | Discontinue study drug. |
| Any hematological or non-hematological toxicity requiring interruption for ≥ 4 weeks | Discontinue study drug. |

* Grade 3 hyperlipidemia (hypercholesterolemia and/or hypertriglyceridemia) should be managed using medical therapies.

Management of stomatitis/oral mucositis/mouth ulcers

Stomatitis/oral mucositis/mouth ulcers due to study drug should be treated using local supportive care. Please note that investigators in earlier trials have described the oral toxicities associated with study drug as mouth ulcers, rather than mucositis or stomatitis. If your examination reveals mouth ulcers rather than a more general inflammation of the mouth, please classify the adverse event as such. Please follow the paradigm below for treatment of stomatitis/oral mucositis/mouth ulcers:

1. For mild toxicity (Grade 1), use conservative measures such as **non-alcoholic mouth wash or salt water (0.9%) mouth wash** several times a day until resolution.
2. For more severe toxicity (Grade 2 in which case patients have pain but are able to maintain adequate oral alimentation, or Grade 3 in which case patients cannot maintain adequate oral alimentation), the suggested treatments are **topical analgesic**

mouth treatments (i.e., local anesthetics such as benzocaine, butyl aminobenzoate, tetracaine hydrochloride, menthol, or phenol) with or without topical corticosteroids, such as triamcinolone oral paste 0.1% (Kenalog in Orabase®).

3. Agents containing hydrogen peroxide, iodine, and thyme derivatives may tend to worsen mouth ulcers. It is preferable to avoid these agents.
4. Antifungal agents must be avoided unless a fungal infection is diagnosed. In particular, systemic imidazole antifungal agents (ketoconazole, fluconazole, itraconazole, etc.) should be avoided in all patients due to their strong inhibition of metabolism of study drugs, thereby leading to higher drug level exposures. Therefore, topical antifungal agents are preferred if an infection is diagnosed. Similarly, antiviral agents such as acyclovir should be avoided unless a viral infection is diagnosed. Note: Stomatitis/oral mucositis should be appropriately graded using the functional grading given on the NCI-CTC for adverse events, version 4.0.

Management of hyperlipidemia and hyperglycemia

Treatment of hyperlipidemia should take into account the pre-treatment status and dietary habits. Blood tests to monitor hyperlipidemia must be taken in the fasting state. Grade 2 hypercholesterolemia (> 300 mg/dL or 7.75 mmol/L) or Grade 2 hypertriglyceridemia (>2.5 x ULN) should be treated with a 3-hydroxy-3-methyl-glutaryl (HMG)-CoA reductase inhibitor (e.g., atorvastatin, pravastatin) or appropriate lipid-lowering medication, in addition to diet. Patients should be monitored clinically and through serum biochemistry for the development of rhabdomyolysis and other adverse events as required in the product label/data sheets for HMG-CoA reductase inhibitors.

Note: Concomitant therapy with fibrates and an HMG-CoA reductase inhibitor is associated with an increased risk of a rare but serious skeletal muscle toxicity manifested by rhabdomyolysis, markedly elevated creatine kinase (CPK) levels and myoglobinuria, acute renal failure and sometimes death. The risk versus benefit of using this therapy should be determined for individual patients based on their risk of cardiovascular complications of hyperlipidemia.

Grade 3 **hyperglycemia** has been observed in patients receiving everolimus therapy. It is suggested that optimal glucose control should be achieved before starting a patient on everolimus and should be monitored during everolimus therapy.

Table 5 - Management of non-infectious pneumonitis

| Worst Grade Pneumonitis | Required Investigations | Management of Pneumonitis | Everolimus Dose Adjustment |
|-------------------------|---|---|--|
| Grade 1 | CT scans with lung windows and pulmonary function testing including: spirometry, DLCO, and room air O ₂ saturation at rest. Repeat chest x-ray/CT scan every 2 Cycles until return to baseline. | No specific therapy is required | Administer 100% of everolimus dose. |
| Grade 2 | CT scan with lung windows and pulmonary function testing including: spirometry, DLCO, and room air O ₂ saturation at rest. Repeat each subsequent Cycle until return to baseline. Consider bronchoscopy * | Symptomatic only. Prescribe corticosteroids if cough is troublesome. | Hold everolimus dose until recovery to ≤ Grade 1. Restart everolimus at a reduced dose (only if patient recovers to Grade 1 within 3 weeks and only if the patient shows evidence of clinical benefit from the agent) Patients will be withdrawn from the study if they fail to recover to ≤ Grade 1 within 3 weeks. |
| Grade 3 | CT scan with lung windows and pulmonary function testing including: spirometry, DLCO, and room air O ₂ saturation at rest.; Repeat each subsequent Cycle until return to baseline. Bronchoscopy is recommended * | Prescribe corticosteroids if infective origin is ruled out. Taper as medically indicated. | Hold treatment until recovery to ≤ Grade 1. May restart protocol treatment within 3 weeks at a reduced dose (by one level) if evidence of clinical benefit. Patients will be withdrawn from the study if they fail to recover to ≤ Grade 1 within 3 weeks. |
| Grade 4 | CT scan with lung windows and required pulmonary function testing includes: spirometry, DLCO, and room air O ₂ saturation at rest. Repeat each subsequent Cycle until return to baseline. Bronchoscopy is recommended *. | Prescribe corticosteroids if infective origin is ruled out. Taper as medically indicated. | Discontinue treatment. |

*A bronchoscopy with biopsy and/or bronchoalveolar lavage is recommended.

